# 6.6 Discontinuation of study treatment and withdrawal of subjects from the study

Premature discontinuation of the clinical trial may occur due to a decision of the regulatory authorities, due to a change in the opinion of the Clinical Research Ethics Committees, due to safety and / or drug problems or indications of ineffectiveness.

It will be considered that there is a voluntary abandonment of the trial due to the refusal of the patient or legal guardian of the same to continue with the treatment or in the study, and the subject will be considered as abandonment immediately after communicating his decision to the Investigator. A patient may discontinue the trial at any time if the person, the legal representative, the investigator or the motorization committee determine that it is not in the best interest of the patient to maintain their participation.

Other reasons for discontinuation include:

- Patients with low compliance with the study drug, below 80%
- Patients requiring hospitalization for worsening psychotic disorder and / or behavioural disturbances associated with psychotic disorder.
- Patients in whom, during the study period, there is a high risk of detected suicide, according to the criteria established by Columbia University according to the risk assessment with the C-SSRS scale.
- Female patients who test positive for urine pregnancy at any time during their participation in the study.
- Any serious adverse event that recommends withdrawal at the discretion of the investigator with the agreement of the monitoring committee.
- The patient decides not to continue with the trial.
- Others: The researcher, as well as the sponsor, reserve the right to interrupt the study at any time for reasonable medical and / or administrative reasons.

Patients who drop out after randomization will not be replaced.

Patients who terminate treatment prematurely will complete an early termination interview and a safety visit.

The patient who has completed the protocol is considered to be one who has completed all the visits included in the 52-week follow-up period.

The interruption of the treatment does not imply that the case is excluded from the statistical analysis. These subjects will be part of the study and will be taken into account when analyzing the data.

There may be other circumstances for the abandonment, which in its case the researcher must make sure that the patient has abandoned the study, and will verify the causes of said abandonment.

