#### 7.3.1 Due to efficacy criteria

## Trial withdrawal Criteria

- Patients with a level of compliance with the study drug lower than 80%
- Patients in whom at some point during the study period a high risk of suicide is detected, according to the criteria established by Columbia University according to the evaluation of said risk using the C-SSRS scale
- Female patients who have a positive urine pregnancy test throughout their participation in the study
- Patients who have a seizure during their participation in the study.
- Patients who, during the period with Vortioxetine, require treatment with another antidepressant different from the study medication.
- Patients who require some treatment contraindicated with the use of Vortioxetine during the study.

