## 8.2. 3 Methods of fertility control

Women of childbearing potential must have documentation of a negative pregnancy test prior to administration of study medication.

Women are not considered of childbearing age if they have had a total hysterectomy and / or bilateral tubal ligation or hysteroscopic sterilization (documentation for surgeries must be provided prior to inclusion) or are in a postmenopausal state (i.e. women who have stopped menstruating for ≥24 months with no alternative causes) or women with premature ovarian failure.

All women of childbearing potential and men who may father children must agree to abstain from sexual intercourse or use highly effective contraception during the study and for at least 30 days after completing study drug dosing.

A highly effective contraceptive method is defined as one that results in a low failure rate (i.e. <1% per year) when used consistently and correctly.

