# 9.- SCHEDULED VISITS AND EVALUATIONS

Procedures PERIOD 1	Visit 1 (- 30 days) Screening	Visit 2 (Day1) Baseline	Visit 3 (Day 8±3) Week 1	Visit 4 (Day 29±3) Week 4	Visit 5 (Day 57±3) Week 8	Visit 6 (Day 85±3) Week 12	Visit 7 (Day 113±3) Week 16	Visit 8 (Day 141±3) Week 20	Visit 9 (Day 169±3) Week 24 
Informed Consent / ACE	X								
Inclusion/Exclusion Criteria	Х	X							
Randomization		X							
Pregnancy Test	X	Х							
Medical History	X	Х	Х	Х	Х	Х	Х	Х	X
HAMD-17 	X								
BARS 	X								
PANSS 	X								Х
SAS 	X	Х	Х	X	X	X	X	Х	Х
SANS 		Х		Х		Х			X
BACS 		Х				Х			Х
BACS App 		Х							Х
NSA-4 		Х		Х		Х			X
GAF 		Х				Х			X
Vitals Signs: weigth, Height, Blood Pressure, Pulse Rate, abdominal perimeter		Х		Х		Х			Х

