#### CAVES PROTOCOL CONFIDENTIAL VERSION 1.0

Hematology/Chemistry 		Х							Х
Dispense Treatment 11		Х	Х	Х	Х	Х	Х	Х	
Compliance 12			Х	Х	Х	Х	Х	Х	Х
Concomitant Medication	X	Х	Х	Х	Х	Х	Х	Х	Х
Adverse Events			Х	Х	Х	Х	Х	Х	Х

- 1. Between week 24 and week 26 the first wash period takes place. The washing time between one period and another will be 2 weeks
- 2. HAMD-17: Hamilton Rating Scale for Depression
- 3. BARS: Behaviorally Anchored Rating Scale
- 4. PANSS: Positive and Negative Syndrome Scale
- 5. SAS: Sedation-Agitation Scale
- 6. SANS: Scale for Assessment of Negative Symptoms
- 7. BACS: Brief Assessment of Cognition in Schizophrenia
- 8. BACS App: Brief Assessment of Cognition in Schizophrenia App. Versión de la Escala BACS en aplicación para Tablets: facilitará la realización de pruebas repetidas y reducirá efectos de la práctica. Existen diferentes versiones de la prueba.
- 9. NSA-4: Negative Symptom Assessment (4-Item)
- 10. GAF: Global Functionality Assessment Scale
- 11. Vortioxetine dosage according to Summary of Product Characteristics (section 6.5 of protocol)
- 12. Patient must bring test medication at each visit for counting. Empty boxes will stay in the center
- 13. Complete blood count including leukocyte, neutrophil, hemoglobin, and platelet counts. Blood chemistry that includes the determination of sodium, potassium, creatinine, urea, lipid profile, glycemia.

CAVES PROTOCOL CONFIDENTIAL VERSION 1.0

Procedures PERIOD 2	Visit10 (Day 183±3) Week 26	Visit11 (Day 190±3) Week 27	Visit12 (Day 211±3) Week 30	Visit13 (Day 239±3) Week 34	Visit14 (Day 267±3) Week 38	Visit15 (Day 295±3) Week 42	Visit16 (Day 323±3) Week 46	Visit17 (Day 351±3) Week 50 	Visit18 (Day 379±3) Week 52
Pregnancy Test	Х								X
Medical History	Х	Х	Х	X	Х	Х	Х	Х	X
HAMD-17	Х								
BARS	Х								
PANSS	Х							Х	Х
SAS	Х	Х	X	X	Х	Х	Х	Х	
SANS	X		X		Х			Х	
BACS	X				Х			X	Х
BACS App	X							X	
NSA-4	X		X		Х			X	
GAF	X				Х			X	Х
Vitals Signs: weigth, Height, Blood Pressure, Pulse Rate, abdominal perimeter	х		х		Х			х	Х
Hematology/Chemistry	X							X	Х
Dispense Treatment	X	Х	X	Х	Х	X	X		
Compliance		Х	X	Х	Х	Х	X	X	
Concomitant Medication	X	Х	X	Х	Х	X	X	X	Х
Adverse Events	X	X	X	X	Х	X	X	X	X

1. Between week 50 and week 52 the second wash period takes place. The visit corresponding to week 52 corresponds to the FINAL VISIT OF THE TRIAL.

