# 9.1.10 Visit 10 (Week 26: day 183 ± 3 days)

- In the case of women of childbearing age, a urine or blood pregnancy test will be requested (the most feasible)
- Physical examination: weight, blood pressure, heart rate, respiratory rate, temperature and abdominal perimeter
- Blood extraction (hemogram and biochemistry)
- HAMD-17
- Clinical, cognitive and functional evaluation: BARS, PANSS, SAS, SANS, BACS, BACS App, NSA-4 and GAF
- Medication administration (day 1 of treatment)
- Review of concomitant medication
- Review of adverse events

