#### 9.1.19 Unscheduled Visit

If a patient presents changes in their marked clinical status or there is a suspicion of an adverse event, an assessment (less than 24 hours) should be made of the need for an unscheduled visit.

To do this, the patient must have a telephone number to contact the research team in case of need due to recurrence of symptoms and an adverse event.

In the unscheduled visit the following procedures will be carried out:

- In the case of women of childbearing age, a urine or blood pregnancy test will be requested (the most feasible)
- Physical examination: weight, blood pressure, heart rate, respiratory rate, temperature and abdominal girth
- Blood extraction (hemogram and biochemistry)
- HAMD-17

- Clinical, cognitive and functional assessment: BARS, PANSS, SAS, SANS, BACS, BACS App, NSA-4 and GAF
- Adherence to treatment
- Concomitant medication review
- Review of adverse events

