# 11. 10 Pregnancy

Subjects will be instructed to notify the investigator of the pregnancy if it occurs, and the subject will immediately exit the study.

In the event of any pregnancy occurring during the development of the study, the researcher will notify the promoter or whoever assumes the tasks delegated by the promoter within 24 hours of their knowledge. Likewise, the pregnancy will be monitored to document its outcome and the newborn's health status. If the outcome of the pregnancy meets the criteria for SAE or if the newborn presents a serious event, the procedures described for the notification of SAE will be followed.

The notification will be made using the specific SAE notification form which will be sent by fax or email to the same contact that will receive the notifications from SAE. The PhV-UICEC-HUVR department will notify within 24 hours of their knowledge to the LundBeck laboratory.

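### No pregnancy test is scheduled while vortioxetine is being taken, in either sequence, although a positive test at any point requires withdrawal

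*Protocol*

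**What the plan says.** Two sections make a positive test a reason to stop. Section 6.6 lists "Female patients who test positive for urine pregnancy at any time during their participation in the study", and the withdrawal criteria in section 7.3.1 list "Female patients who have a positive urine pregnancy test throughout their participation in the study". Section 11.10 adds: "Subjects will be instructed to notify the investigator of the pregnancy if it occurs, and the subject will immediately exit the study".

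On testing, section 8.2.3 states: "Women of childbearing potential must have documentation of a negative pregnancy test prior to administration of study medication". The schedule tables in section 9 mark the test at Visit 1 (screening), Visit 2 (day 1), Visit 10 (day 183, week 26) and Visit 18 (day 379, week 52). The Visit 10 list in section 9.1.10 confirms it: "In the case of women of childbearing age, a urine or blood pregnancy test will be requested (the most feasible"). The tables and the visit-by-visit lists agree that no test is planned at Visits 3 to 9 or Visits 11 to 17.

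Section 9.1.19 also includes a test at an unscheduled visit. The need for such a visit is assessed under this condition: "If a patient presents changes in their marked clinical status or there is a suspicion of an adverse event".

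**The concern.** The withdrawal rule in sections 6.6 and 7.3.1 is triggered by a test result, and it is meant to apply for the whole of participation. The schedule supplies results only before dosing starts and after it has ended. While the drug is being taken, the rule has no scheduled input.

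The consequence is for patient safety. A pregnancy that begins on vortioxetine, and that the woman neither recognises nor reports, could stay exposed until the course ends. The protocol itself treats this as a risk worth managing: it notes pregnancy category C in section 4, requires highly effective contraception and a negative pre-dose test in section 8.2.3, and requires immediate exit in section 11.10. The 24-hour notification period in section 11.10 starts only when the investigator learns of the pregnancy, so late detection also delays reporting and follow-up.

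The primary endpoint, the sample size and the analysis are not affected.

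**Working it through.** The protocol gives no figure to reproduce on this point. The check sets the testing dates against the dosing dates.

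**Inputs (section 9 tables and section 9.1)**

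- Tests: screening, day 1, day 183 and day 379.
- Dosing, vortioxetine first: day 1 to Visit 9, headed "Visit 9 (Day 169±3) Week 24".
- Dosing, TAU first: day 183 (Visit 10) to day 351 (Visit 17, week 50).
- Final test: the visit headed "Visit18 (Day 379±3) Week 52". Its two labels disagree. Week 26 is day 183 and week 50 is day 351, so week 52 would be day 365. Both readings are carried below.

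**Tests set against dosing**

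| | Vortioxetine first | TAU first |
|---|---|---|
| Pre-dose test | day 1 | day 183 |
| Last dose | day 169 | day 351 |
| Length of dosing | 169 − 1 = 168 days | 351 − 183 = 168 days |
| Next scheduled test | day 183 | day 379 (or day 365) |
| Gap between tests | 183 − 1 = 182 days | 379 − 183 = 196 days, or (52 − 26) × 7 = 182 days |
| Scheduled tests between first and last dose | 0 | 0 |

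**Visit windows**

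- Vortioxetine first: the latest Visit 9 is day 169 + 3 = 172, and the earliest Visit 10 is day 183 − 3 = 180.
- TAU first: the latest Visit 17 is day 351 + 3 = 354, and the earliest Visit 18 is day 379 − 3 = 376, or 365 − 3 = 362.

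In every case the next test comes after dosing has ended.

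**Missed opportunities.** The tables mark re-dispensing at six on-drug visits in each period (weeks 1, 4, 8, 12, 16 and 20, or weeks 27, 30, 34, 38, 42 and 46), none with a test.

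**Expected conceptions on drug** = women at risk × annual rate × 24/52

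- All 37 patients of childbearing potential, at the upper bound of 1% per year from section 8.2.3: 37 × 0.01 × 24/52 = 0.171, so below about 0.17.
- Half of them (assumption): 18.5 × 0.01 × 24/52 = 0.085, so below 0.09.
- Half of them, with imperfect use at 5% per year (assumption): 18.5 × 0.05 × 24/52 = 0.427, about 0.43.

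**Longest untested stretch of dosing at nominal visit dates**

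- As written: 168 days.
- Tests at weeks 4, 8, 12, 16 and 20 (or 30, 34, 38, 42 and 46): 4 × 7 = 28 days.
- Tests at weeks 4 and 12 only (or 30 and 38): (24 − 12) × 7 = 84 days.

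**The case against.** The strongest reply is that nothing here is contradictory. Sections 6.6 and 7.3.1 say what follows if a test is positive; they promise no testing interval, and a four-weekly standard appears nowhere in the protocol. The required pre-dose test is in place for both sequences. Inclusion criterion 12 and section 8.2.3 demand highly effective contraception. After baseline, on-drug visits are at most four weeks apart, each with medical history and adverse-event review, and weight and abdominal perimeter are measured at some of them. The expected number of conceptions is well below one, the 5% failure rate is an assumption, and 168 days is a worst case. The only fetal-risk statement in the available text is the pregnancy category, because the product summary in Annex IV is not reproduced.

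Much of this stands, and it bears on priority. The point is a weak design choice and not an internal contradiction, and the absolute risk is low. It does not remove the gap. History and adverse-event review are still self-report, prompted by a question. Weight and girth are not pregnancy tests. Contraception lowers the number of pregnancies but does not detect one. It is also fair to say that testing only at weeks 4 and 12 would leave the last 84 days, half the exposure, without a test.

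**Conclusion.** The concern holds. The number of scheduled pregnancy tests between first and last vortioxetine dose is 0 in both sequences, and neither the visit windows nor the reading of the week 52 visit changes that. The interval from the pre-dose test to the next one is 182 days for vortioxetine first, and 182 or 196 days for TAU first.

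This is a safety-monitoring gap of low probability, and it should be closed because closing it is easy. The count of tests rests on the schedule alone. The expected numbers of conceptions rest on the contraceptive failure rate and on the share of women of childbearing potential, which the protocol does not give.

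**What to change.** For women of childbearing potential, mark a urine pregnancy test in the section 9 tables, and in the matching visit lists of section 9.1, at existing on-drug visits before the next supply is dispensed:

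- vortioxetine in period 1: weeks 4, 8, 12, 16 and 20;
- vortioxetine in period 2: weeks 30, 34, 38, 42 and 46.

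At minimum, test at weeks 4 and 12, or weeks 30 and 38. In the same amendment, add the day 1 test to the Visit 2 list in section 9.1.2, where it is missing although the table marks it.

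The cost is at most 5 strips per woman, or 2 in the minimum version. Even if all 37 patients were women of childbearing potential, that is 37 × 5 = 185 strips, or 37 × 2 = 74. No visit or blood draw is added. The downside is a few extra tests per woman and a protocol amendment.

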# 7.3.2 Due to safety criteria

- Any adverse event described in the technical data sheet of the product that at the discretion of the clinician forces the withdrawal of the study
- When, for any reason, the treatment is no longer safe for the patient
- Any other reason that could endanger the life of the patient or have serious consequences for the same

# 7.3.3 For breach or violation of the rules contained in the protocol

When the patient no longer complies with the rules of the trial, they may be withdrawn at the discretion of the responsible investigator or due to loss of follow-up.

# 7.3.4 Follow-up of prematurely withdrawn patients

If a patient is withdrawn from the trial prematurely, the investigator will provide the main reason for the suspension and, as indicated by the GCP guidelines, the procedures will be followed according to the usual treatment protocols for their pathology at the discretion of the responsible clinician.

#### 8.- TREATMENT OF SUBJECTS

## **Experimental Group**

The experimental group will be based on including Vortioxetine as an adjunct drug to the usual antipsychotic treatment that the subject is taking.

The route of administration of vortioxetine is oral in a single daily dose.

It will start with 10 mg / day for the first 2 weeks, followed by 20 mg / day for the remainder of the study. The vortioxetine dose may be reduced to 5 mg or 10 mg for reasons of tolerability at the discretion of the physician.

# **Control group**

In the case of being included in the control group, patients will be treated according to usual clinical practice that includes the use of antipsychotics according to the indications in their technical data sheet.

The most convenient habitual antipsychotic treatment will be chosen according to the criteria of the prescribing physician.

# 8.1 Treatment duration and adjustments

- The duration of treatment in each arm will be 24 weeks
- To avoid carry-over effects of the medication, a 2-week washout phase will be needed from week 24 to week 26, and another 2-week washout phase at the end of the study (week 50 to 52)
- The trial will last 52 weeks in total

# 8.2 Concomitant medication

Any concomitant medication must be reflected in the CRD (product, dose, route, day of administration, reason for treatment, etc.) throughout the study follow-up period.

#### 8.2.1 Allowed medications

- Oral contraceptives and other hormonal methods; Oral contraceptives must have been started 30 days before the inclusion of the patient.
- Benzodiazepines.

# 8.2.2 Prohibited medications

The following medications will be prohibited for the duration of the study:

- Antidepressant medications
- Clozapine
- Drugs that are contraindicated with the use of vortioxetine or that have a potential interaction with vortioxetine.
- Inducers or inhibitors of cytochrome P450 (CYP) 1A2 (medications, over-thecounter agents, or dietary supplements) from 30 days prior to randomization and during follow-up.
- Anticholinergics

## 8.2. 3 Methods of fertility control

Women of childbearing potential must have documentation of a negative pregnancy test prior to administration of study medication.

Women are not considered of childbearing age if they have had a total hysterectomy and / or bilateral tubal ligation or hysteroscopic sterilization (documentation for surgeries must be provided prior to inclusion) or are in a postmenopausal state (i.e. women who have stopped menstruating for ≥24 months with no alternative causes) or women with premature ovarian failure.

All women of childbearing potential and men who may father children must agree to abstain from sexual intercourse or use highly effective contraception during the study and for at least 30 days after completing study drug dosing.

A highly effective contraceptive method is defined as one that results in a low failure rate (i.e. <1% per year) when used consistently and correctly.

#### These methods include:

- Combined hormonal contraception (containing estrogens and progestogens) associated with inhibition of ovulation
  - oral
  - intravaginal
  - transdermal
- Progestin-only hormonal contraception associated with inhibition of ovulation
  - oral
  - injectable

- implantable: Intrauterine Device (IUD)
- Intrauterine hormone releasing system (IUS)
- Bilateral tubal occlusion
- Vasectomized couple, provided that this partner is the only sexual partner of the woman participating in the trial of childbearing age and that the vasectomized couple has received a medical evaluation of surgical success.
- Sexual abstinence is considered a highly effective method only if it is defined as abstaining from heterosexual intercourse for the entire risk period associated with the study treatments. The reliability of sexual abstinence should be assessed in relation to the duration of the clinical trial and the preferred and usual lifestyle of the subject.

NOTE: Contraceptive methods that are not considered highly effective:

- Progestin-only oral hormonal contraception, where inhibition of ovulation is not the primary mode of action
- Male or female condom with or without spermicide
- Cap, diaphragm or sponge with spermicide

#### 8.3 Rescue medication

The use of rescue medication is not planned. If a patient is withdrawn due to lack of efficacy or some similar condition, they will be treated according to the clinical guidelines and the usual clinical practice for these cases.

# 9.- SCHEDULED VISITS AND EVALUATIONS

Procedures PERIOD 1	Visit 1 (- 30 days) Screening	Visit 2 (Day1) Baseline	Visit 3 (Day 8±3) Week 1	Visit 4 (Day 29±3) Week 4	Visit 5 (Day 57±3) Week 8	Visit 6 (Day 85±3) Week 12	Visit 7 (Day 113±3) Week 16	Visit 8 (Day 141±3) Week 20	Visit 9 (Day 169±3) Week 24 
Informed Consent / ACE	X								
Inclusion/Exclusion Criteria	Х	X							
Randomization		X							
Pregnancy Test	X	Х							
Medical History	X	Х	Х	Х	Х	Х	Х	Х	X
HAMD-17 	X								
BARS 	X								
PANSS 	X								Х
SAS 	X	Х	Х	X	X	X	X	Х	Х
SANS 		Х		Х		Х			X
BACS 		Х				Х			Х
BACS App 		Х							Х
NSA-4 		Х		Х		Х			X
GAF 		Х				Х			X
Vitals Signs: weigth, Height, Blood Pressure, Pulse Rate, abdominal perimeter		Х		Х		Х			Х

#### CAVES PROTOCOL CONFIDENTIAL VERSION 1.0

Hematology/Chemistry 		Х							Х
Dispense Treatment 11		Х	Х	Х	Х	Х	Х	Х	
Compliance 12			Х	Х	Х	Х	Х	Х	Х
Concomitant Medication	X	Х	Х	Х	Х	Х	Х	Х	Х
Adverse Events			Х	Х	Х	Х	Х	Х	Х

- 1. Between week 24 and week 26 the first wash period takes place. The washing time between one period and another will be 2 weeks
- 2. HAMD-17: Hamilton Rating Scale for Depression
- 3. BARS: Behaviorally Anchored Rating Scale
- 4. PANSS: Positive and Negative Syndrome Scale
- 5. SAS: Sedation-Agitation Scale
- 6. SANS: Scale for Assessment of Negative Symptoms
- 7. BACS: Brief Assessment of Cognition in Schizophrenia
- 8. BACS App: Brief Assessment of Cognition in Schizophrenia App. Versión de la Escala BACS en aplicación para Tablets: facilitará la realización de pruebas repetidas y reducirá efectos de la práctica. Existen diferentes versiones de la prueba.
- 9. NSA-4: Negative Symptom Assessment (4-Item)
- 10. GAF: Global Functionality Assessment Scale
- 11. Vortioxetine dosage according to Summary of Product Characteristics (section 6.5 of protocol)
- 12. Patient must bring test medication at each visit for counting. Empty boxes will stay in the center
- 13. Complete blood count including leukocyte, neutrophil, hemoglobin, and platelet counts. Blood chemistry that includes the determination of sodium, potassium, creatinine, urea, lipid profile, glycemia.

CAVES PROTOCOL CONFIDENTIAL VERSION 1.0

Procedures PERIOD 2	Visit10 (Day 183±3) Week 26	Visit11 (Day 190±3) Week 27	Visit12 (Day 211±3) Week 30	Visit13 (Day 239±3) Week 34	Visit14 (Day 267±3) Week 38	Visit15 (Day 295±3) Week 42	Visit16 (Day 323±3) Week 46	Visit17 (Day 351±3) Week 50 	Visit18 (Day 379±3) Week 52
Pregnancy Test	Х								X
Medical History	Х	Х	Х	X	Х	Х	Х	Х	X
HAMD-17	Х								
BARS	Х								
PANSS	Х							Х	Х
SAS	Х	Х	X	X	Х	Х	Х	Х	
SANS	X		X		Х			Х	
BACS	X				Х			X	Х
BACS App	X							X	
NSA-4	X		X		Х			X	
GAF	X				Х			X	Х
Vitals Signs: weigth, Height, Blood Pressure, Pulse Rate, abdominal perimeter	х		х		Х			х	Х
Hematology/Chemistry	X							X	Х
Dispense Treatment	X	Х	X	Х	Х	X	X		
Compliance		Х	X	Х	Х	Х	X	X	
Concomitant Medication	X	Х	X	Х	Х	X	X	X	Х
Adverse Events	X	X	X	X	Х	X	X	X	X

1. Between week 50 and week 52 the second wash period takes place. The visit corresponding to week 52 corresponds to the FINAL VISIT OF THE TRIAL.

